## **2. OBJECTIVES AND HYPOTHESIS**

### **2.1. Objectives**

#### **Primary Objective**

The primary objective is to assess the safety and tolerability of different vaccination schedules of Ad26.ZEBOV and MVA-BN-Filo administered IM as heterologous prime-boost regimens on Days 1 and 29, Days 1 and 57, or Days 1 and 85, in healthy adults, including elderly subjects, and on Days 1 and 29 and Days 1 and 57 in HIV-infected subjects and healthy children in 2 age strata.

#### **Secondary Objectives**

The secondary objectives are:

- To assess humoral immune responses, as measured by ELISA, to the EBOV GP at 21 days post boost of different vaccination schedules of Ad26.ZEBOV and MVA-BN-Filo administered IM as heterologous prime-boost regimens on Days 1 and 29, Days 1 and 57, or Days 1 and 85, in healthy adults, including elderly subjects, and on Days 1 and 29 and Days 1 and 57 in HIV-infected subjects and healthy children in 2 age strata.
- To assess the safety and tolerability of a third vaccination with Ad26.ZEBOV administered at least 1 year post prime in a subset of approximately 90 healthy adults, including elderly subjects, in Cohort 1 (Groups 1 and 2).

#### **Exploratory Objectives**

The exploratory objectives are:

- To assess humoral immune responses, as measured by ELISA, to the EBOV GP at other relevant time points of different vaccination schedules of Ad26.ZEBOV and MVA-BN-Filo administered IM as heterologous prime-boost regimens on Days 1 and 29, Days 1 and 57, or Days 1 and 85, in healthy adults, including elderly subjects, and on Days 1 and 29 and Days 1 and 57 in HIV-infected subjects and healthy children in 2 age strata.

- To assess the neutralizing capacity of the EBOV GP-specific humoral immune responses, as measured by virus neutralization assay, to the EBOV GP of different vaccination schedules of Ad26.ZEBOV and MVA-BN-Filo administered IM as heterologous prime-boost regimens on Days 1 and 29, Days 1 and 57, or Days 1 and 85, in healthy adults, including elderly subjects, and on Days 1 and 29 and Days 1 and 57 in HIV-infected subjects and healthy children in 2 age strata.
- To explore humoral and cellular immune responses to different EBOV GPs and the adenovirus and/or MVA backbone of the various vaccination schedules tested.
- To explore humoral and cellular immune responses to filovirus GPs and/or TAFV NP, if assays are available.
- To assess humoral immune responses, as measured by ELISA, to the EBOV GP at various time points following a third vaccination with Ad26.ZEBOV at least 1 year post prime in approximately 90 healthy adults, including elderly subjects, in Cohort 1 (Groups 1 and 2).

## 2.2. Hypothesis

As this study is designed to provide descriptive information regarding safety and immunogenicity without formal treatment comparisons, no formal statistical hypothesis testing is planned.

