**Table 9: Probability of Observing at Least One Adverse Event Given a True Adverse Event Incidence**

True Adverse Event Incidence (%)	N=55	N=110	N=220	N=440	N=550	N=880
0.1	5%	10%	20%	36%	42%	59%
0.5	24%	42%	67%	89%	94%	99%
1.0	42%	67%	89%	99%	100%	100%
2.5	75%	94%	100%	100%	100%	100%
5.0	94%	100%	100%	100%	100%	100%
10.0	100%	100%	100%	100%	100%	100%

Having immunogenicity data available for 55, 110 or 220 subjects per group on Ad26.ZEBOV or MVA-BN-Filo within a cohort, the following pairwise differences in immune response (ELISA antibody levels against EBOV GP) between vaccine schedules can be detected at any given time point, for a given variability in ELISA antibody levels (**Table 10**).

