**Table 10: Magnitude of Pairwise Difference to be Detected Between Vaccine Regimens for a Given Sample Size**

Variability ELISA antibody levels (SD, $\log_{10}$ scale)	Detectable difference, $\log_{10}$ scale *		
	n1=n2=55	n3=110, n1,n2=220	n1=n2=220
0.3	0.19	0.13	0.11
0.4	0.25	0.18	0.14
0.5	0.31	0.22	0.18

SD: standard deviation

\* 90% power, 5% significant level for 2-sided hypothesis, accounting for multiple testing in Cohort 1

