1.2. Statistical Hypotheses for Trial Objectives

No formal statistical hypothesis testing was planned for this study. This is because the primary purpose of the study was to provide descriptive information regarding safety and immunogenicity of the heterologous prime-boost regimens on Days 1 and 29, Days 1 and 57, or Days 1 and 85 in healthy adults, including elderly subjects, and on Days 1 and 29 or Days 1 and 57 in HIV-infected subjects and healthy children in 2 age strata.

[figure not shown]

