2. GENERAL ANALYSIS DEFINITIONS

The type I error rate (α) is set to 0.05 and corresponding 2-sided 95% confidence intervals (CIs) will be calculated wherever applicable. Adjustment of the α (type I error) level due to multiplicity is not applicable for this study as no planned formal statistical hypothesis testing will be performed.

The analysis is defined separately for each parameter later in this document together with the description of rules for handling missing or incomplete data. The analysis will include vaccinated subjects with respect to the actual vaccine administered. The subjects who received only Ad26.ZEBOV prime vaccination will be included in accordance with the group to which they were randomization. On the other hand, any subject who was vaccinated according to MVA-BN-Filo prime only, MVA-BN-Filo prime/Ad26.ZEBOV boost or a homologous schedule (ie, Ad26.ZEBOV prime/Ad26.ZEBOV boost or MVA-BN-Filo prime/MVA-BN-Filo boost) will be excluded from summary tables and graphs, and listed separately.

In general, the study data will be analyzed as follows:

- Categorical variables will be summarized with a frequency table presenting counts and percentages.
- Continuous variables will be summarized using the following statistics, as appropriate: number of observations, arithmetic mean, geometric mean, corresponding 95% CI, standard deviation, standard error, median, quartiles (Q1 and Q3), minimum and maximum.

Baseline value will be defined as the value of the last available assessment performed prior to the prime vaccination, unless specified otherwise.

For safety assessments, the *baseline value* will be an assessment performed prior or on the date (if only time of assessment is missing) of the prime vaccination. The baseline value for immunogenicity assessments will be an assessment performed before or on the date of the prime vaccination. In case of multiple values, the value closest to the vaccination will be used as the baseline.

Reference value (only for immunogenicity) will be defined as the assessment performed on the date of the boost vaccination. In case of multiple values (on the same day of vaccination), the value closest to the vaccination will be used as the reference value.

Visit day will be determined relative to the actual day of vaccination (ie, date of Doses 1, 2 or 3).

Repeated assessments of immunogenicity and safety will be allocated to analysis windows and periods based on

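### Protocol Table 10 quotes 90% power for two-sided tests, multiplicity-adjusted in Cohort 1, but neither the protocol nor the SAP plans such a test or adjustment

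*Protocol*

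**What the plan says.** **No testing.** Protocol Section 2.2 calls the study descriptive, "without formal treatment comparisons, no formal statistical hypothesis testing is planned". SAP Section 1.2 agrees: "No formal statistical hypothesis testing was planned for this study". SAP Section 2 sets a type I error of 0.05 with two-sided 95% intervals, and says that adjustment of the alpha "level due to multiplicity is not applicable for this study as no planned formal statistical hypothesis testing will be performed".

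**Power for tests.** Protocol Section 11.2, between Tables 9 and 10, begins "Having immunogenicity data available for 55, 110 or 220 subjects per group" and goes on to say that "the following pairwise differences in immune response (ELISA antibody levels against EBOV GP) between vaccine schedules can be detected at any given time point". The Table 10 footnote gives the basis: "90% power, 5% significant level for 2-sided hypothesis, accounting for multiple testing in Cohort 1".

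**What will be analysed.** Protocol Section 11.6 says that differences between schedules will be described at 21 days post-boost, 6 months post-boost and Day 365. SAP Section 6.2.1.3 lists ELISA geometric means, geometric mean fold increases and responder rates, each with a 95% interval, by schedule and time point. It lists no test, ratio or difference interval between schedules.

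**Use.** Protocol Section 11 says that the primary analysis, on Cohort 1, will help to identify the best candidate schedule. SAP Section 1.4 refers back to Protocol Section 11.2 for the sample size justification.

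**The concern.** Power is a property of a decision rule. Table 10 assumes two-sided tests, adjusted for multiple comparisons in Cohort 1. The analysis sections specify no such rule, and the SAP sets the adjustment aside.

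The schedules will still be compared to help choose one, and Table 10 is the only statement of how well the trial can separate them on antibody level. A reader who applies its 90% and 5% to the published intervals may be relying on figures that those intervals do not have.

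**Working it through.** **Inputs.** From Table 10: SD 0.3, 0.4 and 0.5 on the log10 scale (row label "Variability ELISA antibody levels"); active-vaccine groups of 55 v 55, 110 v 220 (column label "n3=110, n1,n2=220") and 220 v 220; 90% power; two-sided 5%. No dropout is applied. The footnote does not name the adjustment method, so three levels were tried.

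**Step 1: reproduce Table 10.** The normal-approximation formula is

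d = (z(1−α/2) + z(0.90)) × SD × √(1/n1 + 1/n2).

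For 55 v 55, SD 0.3, α = 0.05: (1.960 + 1.282) × 0.3 × 0.1907 = 0.185. The noncentral-t version gives 0.187; the printed value is 0.19. Noncentral-t results for SD 0.3 / 0.4 / 0.5:

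| Comparison | Printed | α = 0.05 | α = 0.025 | α = 0.05/3 |
|---|---|---|---|---|
| 55 v 55 | 0.19 / 0.25 / 0.31 | 0.187 / 0.250 / 0.312 | 0.204 / 0.272 / 0.340 | 0.213 / 0.284 / 0.355 |
| 110 v 220 | 0.13 / 0.18 / 0.22 | 0.114 / 0.152 / 0.190 | 0.124 / 0.165 / 0.207 | 0.129 / 0.172 / 0.216 |
| 220 v 220 | 0.11 / 0.14 / 0.18 | 0.093 / 0.124 / 0.155 | 0.101 / 0.135 / 0.168 | 0.106 / 0.141 / 0.176 |

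The 55 v 55 column fits an unadjusted 5% test. The Cohort 1 columns fit a Bonferroni adjustment for three pairs and neither of the other two levels. Eight of nine cells match to two decimals. The exception is SD 0.4 for 110 v 220, printed 0.18 against 0.17, which is on the conservative side.

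**Step 2: what two plausible readings would deliver at the printed differences.**

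*(a) Unadjusted 95% interval for a pairwise difference.* Power = Φ(d / (SD × √(1/n1 + 1/n2)) − 1.96). For 220 v 220, SD 0.4: Φ(0.14 / 0.0381 − 1.96) = 0.956.

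*(b) Non-overlap of the two per-schedule 95% intervals.* Power = Φ((d/SD − 1.96 × (1/√n1 + 1/√n2)) / √(1/n1 + 1/n2)). For 220 v 220, SD 0.4: Φ((0.350 − 1.96 × 0.1348) / 0.0953) = 0.816.

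The chance of at least one false difference among the three Cohort 1 pairs (220, 220, 110) at one time point was found by simulation with equal true means.

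| Reading | Power, 55 v 55 | Power, Cohort 1 pairs | Familywise error, Cohort 1 |
|---|---|---|---|
| Table 10 as printed | 90% | 90% | 5% |
| (a) Difference intervals | 90-91% | 96-97% | 12.1% |
| (b) Non-overlap | 68-71% | 82-87% | 1.7% |

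Cohorts 2a, 2b and 3 have only Groups 1 and 2, so 55 v 55 is a single pair. Reading (a) there has a 5% error.

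**Step 3: precision of the analysis that is planned.** Half-width of one schedule's 95% interval = 1.96 × SD / √n. For n = 55, SD 0.3: 1.96 × 0.3 / 7.416 = 0.079.

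| n | SD 0.3 | SD 0.4 | SD 0.5 |
|---|---|---|---|
| 55 | 0.079 | 0.106 | 0.132 |
| 110 | 0.056 | 0.075 | 0.093 |
| 220 | 0.040 | 0.053 | 0.066 |

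For a pairwise difference, 1.96 × SD × √(1/n1 + 1/n2) gives 0.11 / 0.15 / 0.19 (55 v 55), 0.07 / 0.09 / 0.11 (110 v 220) and 0.06 / 0.07 / 0.09 (220 v 220).

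**The case against.** The strongest reply is that Table 10 is illustrative. The planned 1,056 subjects are justified by the safety database (Protocol Section 11.2, SAP Section 1.4), and safety is the primary objective. Over a range of SDs, Table 10 shows only what the resulting group sizes could resolve, and both documents say plainly that no formal testing is planned. Protocol Section 3.2 also allows for possible statistical comparisons across groups. Much of this stands: no sample size, endpoint or output depends on the table, and its arithmetic is sound apart from one cell.

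It does not remove the inconsistency. Neither Section 11.2 nor the footnote labels the table illustrative, no such comparison is specified anywhere, and the Cohort 1 columns embed an adjustment that the SAP calls not applicable.

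A reader might go further and infer that unadjusted intervals would deliver neither the 90% nor the 5%. That is not supported. Difference intervals keep both figures for 55 v 55 and exceed 90% power in Cohort 1, where only the error rate is inflated. Non-overlap loses power but holds the Cohort 1 error well below 5%. Setting the 12% error of one reading beside the 68-71% power of the other would combine two rules that nobody would apply together.

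**Conclusion.** The point holds as a matter of consistency and interpretation. Table 10's power and adjusted error rate describe tests that neither document plans. In Cohort 1, neither unadjusted reading examined reproduces both figures: difference intervals give 96-97% power with 12% familywise error per time point, and non-overlap gives 82-87% with 1.7%. For 55 v 55, difference intervals would match Table 10, while non-overlap of the intervals actually planned gives 68-71% power.

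These figures assume normal log10 titres with a common SD, the full planned numbers of evaluable active-vaccine recipients, and three pairs in Cohort 1. The three-pair Bonferroni adjustment is inferred from the printed numbers.

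It would be wrong to conclude that the trial is mis-sized. The stated basis for the total is the safety database, and no change in sample size follows. The matter is minor and cheap to correct.

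**What to change.** 1. In Protocol Section 11.2, replace Table 10, its lead-in sentence and its footnote with the expected half-widths of the per-schedule 95% intervals on the log10 scale, as tabulated in Step 3. Drop the references to power, significance level and multiple testing.
2. To deliver the between-schedule description promised in Protocol Section 11.6, add to SAP Section 6.2.1.3 the pairwise ELISA geometric mean ratio with an unadjusted 95% interval at 21 days post-boost, 6 months post-boost and Day 365. Label it descriptive and not adjusted for multiplicity, and state the expected log10 half-widths of the difference from Step 3.

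The cost is one replaced table with its surrounding text, a sentence or two in the SAP, and one added summary at three visits. Sample size and data collection do not change.

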## 3. STUDY DESIGN AND RATIONALE

### 3.1. Overview of Study Design

This is a randomized, observer-blind, placebo-controlled, parallel-group, multicenter, Phase 2 study in Africa to evaluate the safety, tolerability and immunogenicity of different heterologous prime-boost regimens using Ad26.ZEBOV at a dose of  $5 \times 10^{10}$  vp as prime and MVA-BN-Filo at a dose of  $1 \times 10^8$  Inf U (nominal titer) as boost at a 28-, 56- or 84-day interval in healthy adult and elderly subjects. The same prime-boost schedules, except for the 84-day interval, will be evaluated in HIV-infected subjects and healthy children in 2 age strata. At selected sites in Cohort 1 (Groups 1 and 2), a third vaccination with Ad26.ZEBOV will be administered at least 1 year post prime to subjects who consent to this (Cohort 1 substudy). Subjects who received a late boost vaccination or did not receive the boost vaccination at all due to a study pause will not be included in the Cohort 1 substudy.

This study will enroll a planned total number of 1,056 subjects, who have never received a candidate Ebola vaccine and have no prior exposure to Ebola virus (including travel to epidemic Ebola areas less than 1 month prior to screening) or a diagnosis of Ebola virus disease.

The study is comprised of 3 cohorts, which will be enrolled sequentially (see [Figure 1](#)): healthy adult and elderly subjects (aged 18 to 70 years inclusive, Cohort 1), HIV-infected subjects (aged 18 to 50 years inclusive, Cohort 2a) and healthy children in 2 age strata (adolescents aged 12 to 17 years inclusive, Cohort 2b; children aged 4 to 11 years inclusive, Cohort 3). The prime-boost regimens that will be evaluated in this study will differ only in the timing of the boost vaccination (ie, 28, 56 or 84 days after prime, respectively referred to as Groups 1, 2 and 3), while the dose of each study vaccine (Ad26.ZEBOV, MVA-BN-Filo or placebo) and the

sequence of prime-boost vaccination will be identical. Groups 1 and 2 will be evaluated in each cohort, while Group 3 (84-day interval) will be evaluated in Cohort 1 only.

In Cohort 1, subjects will be enrolled in parallel and randomized in a 1:1:1 ratio to Groups 1, 2 and 3 at baseline until a target of 132 subjects have been included in Group 3. Afterwards, randomization in this cohort will proceed in a 1:1 ratio to Groups 1 and 2. In Cohorts 2a, 2b, and 3, subjects will be enrolled in parallel and randomized in a 1:1 ratio to Groups 1 and 2 at baseline. Within each group (for all cohorts), subjects will be randomized in a 5:1 ratio to receive Ad26.ZEBOV and MVA-BN-Filo versus placebo.

[figure not shown]
Available interim analysis results of 7-day post-prime safety and immunogenicity data from the ongoing and/or planned Phase 1 studies (studies in Europe, US and Africa) will be provided before the start of the present study, which will start with Cohort 1. Progression to the next cohort will proceed following favorable IDMC review:

- Cohorts 2a and 2b can start when 25% of subjects in Cohort 1 have completed their 7-day post-prime visit.
- Cohort 3 can start when 50% of subjects in Cohort 2b have completed their 7-day post-prime visit.

The real-time monitoring of blinded data will be conducted by the sponsor. The interim data (unblinded) will be provided to and reviewed by the IDMC. The decision to open Cohorts 2a, 2b, and 3 will be based on the sponsor's and the IDMC's review of the interim safety data. Progression to the next cohort will also take into account pre-specified pausing rules (see Section 9.3.2).

A schematic overview of the study design is presented in [Figure 1](#).

**Figure 1: Schematic Overview of the Study**

Number/number: number of subjects per group randomized to Ad26.ZEBOV and MVA-BN-Filo/placebo.

- Cohorts 2a and 2b: starts when 25% of subjects from Cohort 1 have reached the 7-day post-prime visit
- Cohort 3: starts when 50% of subjects from Cohort 2b have reached the 7-day post-prime visit
- \* Subjects who received Ad26.ZEBOV and MVA-BN-Filo will receive Ad26.ZEBOV as third vaccination at least 1 year post prime. Subjects who received placebo will receive placebo as third vaccination at least 1 year post prime.

Within each cohort, study-site personnel (except for those with primary responsibility for study vaccine preparation and dispensing), and subjects will be blinded to the study vaccine allocation until the last subject in that cohort has completed the study. Refer to [Section 5](#) for further details on blinding in case of interim analyses.

The study consists of a screening phase of up to 8 weeks (starting from the moment the subject signs the ICF and/or informed assent), a vaccination phase in which subjects will be vaccinated at baseline (Day 1) followed by a boost vaccination on Day 29, 57 or 85, and a post-vaccination phase and long-term follow-up phase until Day 365. The Cohort 1 substudy consists of a vaccination phase in which subjects will be vaccinated at least 1 year post prime vaccination, a post-vaccination phase, and a long-term follow-up phase until the 1-year post third vaccination visit. All subjects within a cohort will be followed in a blinded manner by the site until the last subject in that cohort has completed the study. Any subject who completed either the 6-month post-prime and/or the Day 365 visit prior to approval of Amendment 2 was required to attend the 6-month post-boost and the Day 365 visit after approval of Amendment 2. Refer to [Section 9.1.6](#) for study procedures that need to be followed in case of a study pause.

The baseline visit may be scheduled as soon as the results of all screening assessments are known (but should occur within 8 weeks from screening, see [Section 9.1.2](#)) and show that the subject is eligible for inclusion. The administration of the prime vaccination will occur on Day 1 (baseline), after the completion of all baseline assessments.

All subjects will receive the study vaccine (Ad26.ZEBOV, MVA-BN-Filo or placebo) through IM injection (0.5 mL) in the deltoid muscle:

- Ad26.ZEBOV ( $5 \times 10^{10}$  vp) on Day 1, followed by a boost vaccination of MVA-BN-Filo ( $1 \times 10^8$  Inf U) on Day 29, 57 or 85; *OR*
- Placebo (0.9% saline) on Day 1, followed by a boost vaccination of placebo (0.9% saline) on Day 29, 57 or 85.

In a substudy at selected sites, approximately 90 healthy adult subjects in Cohort 1 (Groups 1 and 2) will receive a third vaccination with Ad26.ZEBOV at  $5 \times 10^{10}$  vp or placebo at least 1 year post prime vaccination.

Refer to Section 6 for further details on dosage and administration. Subjects will remain at the site for a total of 60 ( $\pm 15$ ) minutes (after prime and boost vaccinations) or 30 ( $\pm 15$ ) minutes (after the third vaccination) post-vaccination to monitor for the development of any acute reactions, or longer if deemed necessary by the investigator (eg, in case of grade 3 adverse events).

The investigators, together with the sponsor's medical monitor, will be responsible for the safety monitoring of the study, and will halt vaccination of further subjects in case any of the pre-specified pausing rules described in Section 9.3.2 have been met. Criteria for postponement of vaccination at the scheduled time for vaccine administration and contraindications to boost and third vaccinations have been defined and will be applied by the investigator (not including those occurring because of study hold) (see Sections 6.2 and 6.3 respectively). Discontinuation of study vaccine should occur in any subject meeting the criteria outlined in Section 10.2.

Safety will be assessed by collection of solicited local and systemic adverse events (reactogenicity), unsolicited adverse events, serious adverse events, and IREs. The subjects will be closely observed by study-site personnel for the first 30 ( $\pm 10$ ) minutes after each vaccination, and again at 60 ( $\pm 15$ ) minutes after prime and boost vaccinations, and any unsolicited, solicited local or systemic adverse events will be documented during this period. Upon discharge from the site, subjects will receive a diary, a thermometer and a ruler to measure solicited local reactions and body temperature. Subjects will be instructed to record solicited local and systemic adverse events in the diary in the evening after each vaccination and then daily for the next 7 days at approximately the same time each day. Diaries should be completed at home by the subject (or parent, legal guardian or caregiver, as applicable). For illiterate subjects or those having difficulty completing the diary independently, the sites will make arrangements to have the diary completed according to their local practice. The investigator will document unsolicited adverse events from signing of the ICF/assent onwards until 42 days post-last vaccination (excluding the third vaccination), and again from the day of the third vaccination until 28 days thereafter for subjects in the Cohort 1 substudy (note: events that started before the third vaccination but are still present at the time of third vaccination should also be recorded). The investigator will document serious adverse events and IREs from signing of the ICF/assent onwards until the end of the study. The primary (or secondary for Cohort 1 substudy) endpoints are adverse events,

serious adverse events, IREs and solicited local and systemic adverse events (see Section 11.1). Other safety assessments include an ECG for subjects  $\geq 18$  years of age (performed at screening), physical examination, vital signs (blood pressure, pulse/heart rate, body temperature), clinical laboratory and pregnancy testing.

In addition, the investigator will collect samples for immunogenicity assessments at the time points indicated in the [Time and Events Schedule](#). Samples to assess humoral responses will be taken from all subjects; samples to assess cellular immune responses will be taken from subjects at selected sites (targeted at 165 subjects [138 Ad26.ZEBOV and MVA-BN-Filo, and 27 placebo] in Cohort 1 and 33 subjects [28 Ad26.ZEBOV and MVA-BN-Filo, and 5 placebo] in each of the other cohorts). Peripheral blood mononuclear cell (PBMC) sampling at selected sites will continue until the targeted number of subjects is reached. Samples to assess cellular immune responses are optional for subjects in the Cohort 1 substudy and may only be collected in a subset of subjects. Subjects giving informed consent for the study will be informed that their leftover blood samples will be stored for potential future research. Subjects participating at selected sites where PBMC samples are collected will be asked explicitly to consent for potential future genetic research to be performed on PBMC samples. Subjects can withdraw consent for their samples to be used for future research at any time (see Section 16.2.5).

The primary analysis will be conducted when all subjects in Cohort 1 have completed the 6-month post-boost visit or discontinued earlier, to aid in the assessment of which vaccination schedule will be the best candidate for future studies and implementation in the field. Study-site personnel, subjects and sponsor personnel involved in subject level data review will remain blinded until the last subject in that cohort has completed the study. Sponsor personnel involved in the conduct of the primary analysis and in making future decisions for the program will be unblinded to the data of Cohort 1, but will remain blinded to the data of the other cohorts.

For the Cohort 1 substudy of subjects who received the third vaccination, an interim analysis may be performed when all subjects have completed the 6-month post third vaccination visit, or discontinued earlier.

In each cohort, after completion of the 6-month post-boost visit by all subjects, an interim analysis will be conducted on safety and selected immunogenicity data and the cohort will be unblinded to the sponsor. Subjects who completed the 6-month post-prime visit prior to approval of Amendment 2 were required to attend the 6-month post-boost visit after approval of Amendment 2.

The final analysis will be performed when all subjects have completed the last study-related visit or discontinued earlier (including subjects participating in the Cohort 1 substudy).

While Cohort 1 was enrolling, the sponsor halted all vaccinations in this study due to the occurrence of a serious and very rare condition, Miller Fisher syndrome, reported in study VAC52150EBL2001 (described in Section 1.1.2.3) until a revised ICF was prepared and approval to restart the study was granted by the relevant competent authority. This interruption in dosing affected over 200 consented subjects, some who were awaiting prime vaccination and

some awaiting boost vaccination. When approval was granted to restart the study under Amendment 1, a late boost vaccination has been offered to those subjects who were out-of-window for the boost vaccination, unless it was prohibited. Those subjects who agreed to the late boost have been following the procedures as outlined in Amendment 1.

All subjects (including placebo) who were primed prior to the pause and did not/will not receive a late boost vaccination are being followed every 3 months after the prime vaccination for safety until Day 365 (see [Additional Time and Events Schedule](#) for subjects who do not receive a boost vaccination because of a study pause). Therefore, non-serious adverse events will be reported until the 42-day post-last vaccination (excluding third vaccination) visit rather than the 42-day post-boost vaccination visit. Serious adverse events and IREs will be reported throughout the study until Day 365 (for details, see Section [9.3.1](#)).

Female subjects who became pregnant with estimated conception within 28 days after vaccination with MVA-BN-Filo (or placebo) or within 3 months after vaccination with Ad26.ZEBOV (or placebo) and children born to vaccinated female subjects who became pregnant with estimated conception within 28 days after vaccination with MVA-BN-Filo (or placebo) or within 3 months after vaccination with Ad26.ZEBOV (or placebo) (unless local regulations have additional requirements for follow-up) will be eligible for enrollment into the VAC52150 Vaccine Development Roll-over study (VAC52150EBL4001) for long-term surveillance (for a total of up to 60 months after the prime vaccination) (see Section [9.1.8](#) for details). After unblinding, only female subjects and the children of female subjects who received Ad26.ZEBOV and/or MVA-BN-Filo will remain in the VAC52150 Vaccine Development Roll-over study for long-term surveillance. After unblinding, female subjects and the children of female subjects who received placebo and have already been enrolled into the VAC52150 Vaccine Development Roll-over study will be discontinued from further participation in the roll-over study.

